#### 3.2 Number of Study Centers

This is a multicenter, multinational study.

### **3.3 Number of Patients**

Approximately 270 patients will be randomized in this study, with approximately 54 patients assigned to each of the 5 treatment cohorts.

### **3.4 Overall Study Duration and Follow-up**

The length of patients' participation in the study may be up to 18 months (72 weeks), which includes a 4-week screening period, an up to 52-week treatment period with Study Drug (ISIS 681257 or placebo), and a 16-week post-treatment follow-up period. The treatment portion of the study will be complete when the last patient reaches 6 months of exposure.

Patients may be required to attend additional visits for monitoring of AEs or abnormal investigation results. The frequency of additional monitoring will be determined by the Study Medical Monitor in consultation with the Investigator.

#### **3.4.1 Screening**

Patient eligibility for the study will be determined within 4 weeks prior to study.

#### **3.4.2 Treatment**

For each patient, minimum treatment duration is 6 months and maximum is 52 weeks.

All patients enrolled will be randomized to a minimum of 6 months of treatment in 1 of 5 treatment cohorts. On completion of the 6 months, patients may continue treatment within the same randomized cohort until the last patient reaches 6 months of exposure (for continuing safety assessments), with a maximal exposure period of 12 months. End of Treatment visits for all patients on treatment will be scheduled no later than the End of Treatment visit of the last patient to complete 6 months of exposure.

The End of Treatment visit should be scheduled one dosing interval post last dose of study drug: one week post last dose for weekly dosing (Cohort E), 2 weeks post last dose for every 2-week dosing (Cohort D), and 4 weeks post last dose for every 4-week dosing (Cohort A-C). The procedures scheduled for the Week 53/ET visit ([Appendix A](#)) will be performed at the End of Treatment visit. Following the End of Treatment visit patients will then enter a 16-week post-treatment follow-up period.

Eligible patients will report to the Study Center for assessments at specified intervals throughout the 52-week treatment period as detailed in the Schedule of Procedures in [Appendix A](#). During the Treatment, Study Drug (ISIS 681257 or placebo) will be administered by SC injection once-weekly, every 2 weeks, or every 4 weeks, depending on cohort assignment.

#### **3.4.3 Post-Treatment**

Patients when completed dosing will enter the 16-week post-treatment follow-up period and will return to the Study Center for 3 follow-up visits 4, 10, and 16 weeks after the treatment period as per [Appendix A](#) (Follow-up).

The final study visit for each patient will be 16 weeks after the treatment period.

### **3.5 End-of-Study**

The End-of-Study is defined as last patient, last visit.

For individual patients, End-of-Study is defined as completion of their last study visit.

### **3.6 Data and Safety Monitoring Board**

An independent Data and Safety Monitoring Board (DSMB) will be assembled to review safety, tolerability and efficacy (as needed) data collected on ISIS 681257 during this study. The DSMB will be constituted to include expertise in medical specialties relevant to the safety of antisense drugs (nephrology, hepatology, hematology and cardiology). Specialist members of the DSMB will be informed and consulted on all treatment-related SAEs relevant to their expertise and all changes of relevant laboratory parameters that trigger stopping rules ([Section 8.6](#)), within 24 hours of receipt of such results. In addition, all accrued safety data relevant to each of medical area specialist will be forwarded monthly for review.

The full DSMB review of all accumulated data will be performed quarterly. Based on its ongoing assessment of the safety and tolerability of ISIS 681257, the DSMB will provide recommendations to the Sponsor for modifying, stopping or continuing the study as planned. Details on the safety assessments, frequency of review, meeting schedules and controlled access to unblinded data are outlined in the DSMB Charter and/or Statistical Analysis Plan (SAP).

## **4. PATIENT ENROLLMENT**

### **4.1 Screening**

Before patients may be enrolled into the study, the Sponsor or designee requires a copy of the Study Center's written independent ethics committee/institutional review board (IEC/IRB) approval of the protocol, informed consent form, and all other patient directed information and/or recruitment material.

Patients or their legally acceptable representatives must sign the consent form before any screening tests or assessments are performed. At the time of consent, the patient will be considered enrolled into the study and will be assigned a unique screening number before any study procedures, including screening procedures, are performed. The screening number and patient identification number must remain constant throughout the entire trial. In the event the patient is re-consented and re-screened the patient must be given a new screening number. Screening numbers and patient identification numbers, once assigned, will not be re-used.

### **4.2 Randomization**

Patients will be randomized after all screening assessments have been completed and after the Investigator has verified that they are eligible per criteria in [Sections 5.1](#) and [5.2](#). No patient may begin treatment prior to randomization and assignment of a unique patient identification number.

Using an Interactive Web-Response System (IXRS), eligible patients will be randomized in a 1:1:1:1:1 ratio to 1 of the 5 parallel-dose cohorts (Cohorts A, B, C, D, or E). Within each dose cohort, patients will be randomized in a 5:1 ratio to receive ISIS 681257 or matching volume of placebo, respectively.

A permuted block schedule will be used. The randomization schedule will be generated and held by an independent vendor.

#### **4.3 Replacement of Patients**

Patients who withdraw from the study will not be replaced.

#### **4.4 Unblinding of Treatment Assignment**

The Sponsor and all patients, monitors, and Study Center personnel related to the study will be blinded throughout the study and until all patients have completed the study and the database has been locked. However, if a patient has suffered a SAE (as defined in [Section 9.3.3](#)), and/or when knowledge of the treatment assignment will impact the clinical management of the patient, the Investigator will have the ability to unblind the treatment assignment for that patient using the IXRS. The Sponsor will determine the point at which all treatment assignments will be unblinded. The Sponsor or designee will be informed of the unblinding of a patient within 24 hours. In addition, all SUSARs will be unblinded by the Sponsor's or designee's Drug Safety and Quality Assurance personnel for the purpose of regulatory reporting (see [Section 9.2](#)).

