#### **9.3.3 Serious Adverse Event (SAE)**

A SAE is any AE that in the view of either the Investigator or Sponsor, meets any of the following criteria:

- Results in death
- Is life threatening, that is, poses an immediate risk of death at the time of the event
- An AE or adverse reaction is considered "life-threatening" if, in the view of either the Investigator or Sponsor, its occurrence places the patient at immediate risk of death. It does not include an AE or adverse reaction that, had it occurred in a more severe form, might have caused death
- Requires inpatient hospitalization or prolongation of existing hospitalization

- Results in a persistent or significant incapacity or substantial disruption of the ability to conduct normal life functions
- Results in a congenital anomaly or birth defect in the offspring of the patient (whether the patient is male or female)
- Important medical events that may not result in death, are not life-threatening, or do not require hospitalization may also be considered serious when, based upon appropriate medical judgment, they may jeopardize the patient and may require medical or surgical intervention to prevent one of the outcomes listed in this definition. Examples of such medical events include allergic bronchospasm requiring intensive treatment in an emergency room or at home, blood dyscrasias or convulsions that do not result in inpatient hospitalization, or the development of drug dependency or drug abuse

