#### 9.4.1 *Serious Adverse Events/Adverse Events of Special Interest*

In the interest of patient safety, and in order to fulfill regulatory requirements, all SAEs and AEs of special interest (regardless of their relationship to Study Drug) should be reported to the Sponsor or designee within 24 hours of the Study Center's first knowledge of the event. The collection of SAEs will begin after the patient signs the informed consent form and stop at the end of the patient's follow-up period. When the Investigator is reporting by telephone, it is important to speak to someone in person versus leaving a message. An Initial Serious Adverse Event Form should be completed and a copy should be emailed or faxed to the Sponsor or designee. The contact information for reporting SAEs is as follows:

**Attention:** [REDACTED]

**Email:** [REDACTED]

**Fax:** [REDACTED]

Detailed information should be actively sought and included on Follow-Up Serious Adverse Event Forms as soon as additional information becomes available. All SAEs will be followed until resolution during the study period. SAEs that remain ongoing past the patient's last protocol-specified follow-up visit will

be evaluated by the Investigator and Sponsor. If the Investigator and Sponsor agree the patient's condition is unlikely to resolve, the Investigator and Sponsor will determine the follow-up requirement.

All SAEs considered treatment-related, as defined in [Section 9.4.3.1](#), will be reported by the Sponsor to the DSMB as described in [Section 3.6](#).

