#### **9.4.3 Evaluation of Adverse Events (Serious and Non-Serious)**

The Investigator's opinion of the following should be documented on the Adverse Event Case Report Form:

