#### **10.1.4 Dose Selection**

Dose selection for the further development will be based on the following efficacy and safety considerations; more than 1 dose may meet these criteria. An effective dose, or dose regimen, will be one that achieves clinically-meaningful reduction in plasma Lp(a) levels. Safety will be evaluated on the basis of incidence of expected and unexpected treatment-related SAEs and other specific safety considerations including the incidence of platelet reductions, and renal or hepatic injury.

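### Section 4.4 lets the investigator break the blind for any SAE, without clinical need and before relatedness is recorded, which can bias the active-versus-placebo contrast in treatment-related SAEs

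*Protocol*

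**What the plan says.** Section 4.4 sets a default of blinding for sponsor, patients, monitors and site staff until all patients have finished and the database is locked. It then makes an exception for the investigator, who may use the IXRS "if a patient has suffered a SAE (as defined in [Section 9.3.3](#)), and/or when knowledge of the treatment assignment will impact the clinical management". The sponsor's part in this is notification after the event: "The Sponsor or designee will be informed of the unblinding of a patient within 24 hours". The section mentions no prior contact, stated reason or clinical need for the SAE condition.

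The SAE definition that Section 4.4 points to is broad. Among its criteria in Section 9.3.3 is "Requires inpatient hospitalization or prolongation of existing hospitalization", whatever the cause.

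Relatedness is one of the items introduced in Section 9.4.3 by "The Investigator's opinion of the following should be documented on the Adverse Event Case Report Form"; its categories are in Section 9.4.3.1.

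The relatedness label is then used in two places. Section 10.1.4 says: "Safety will be evaluated on the basis of incidence of expected and unexpected treatment-related SAEs", alongside other safety considerations. Sections 3.6 and 9.4.1 have treatment-related SAEs reported to the DSMB, and Section 3.6 gives its specialist members a 24-hour route for them.

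**The concern.** The SAE condition adds nothing that patient safety needs. If the assignment matters to how an SAE is managed, the second condition in the sentence already allows the code to be opened. What the first condition adds is unblinding when the assignment does not matter to care. In patients with established coronary, cerebrovascular or peripheral arterial disease, hospital admissions with causes other than study drug are foreseeable, and each would qualify.

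Relatedness is a matter of judgement. The *possible* category turns on whether timing is plausible and whether other explanations suffice. An investigator who knows that a patient is on placebo has little reason to call an event related, and one who knows that a patient is on active drug may be readier to do so. Both shifts widen the apparent difference between active and placebo. At stake is the credibility of the related-SAE comparison in a trial whose primary objective includes safety. This is a rule that the protocol states, and it concerns trial conduct; no statistical analysis plan can restore a blind once it is broken.

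**Working it through.** The protocol gives no figure on this point to reproduce, so the check is first a reading of the text and then a calculation of scale.

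**Reading the chain**

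1. Trigger: Section 4.4, "if a patient has suffered a SAE (as defined in [Section 9.3.3", followed by *and/or* and the clinical-management condition. Either condition alone suffices. The SAE need not be related or unexpected.
2. Who judges: Sections 9.4.3 and 9.4.3.1 assign relatedness to the investigator, who is also the person allowed to open the code.
3. Order of events: neither Section 4.4 nor Sections 9.4.1 to 9.4.3.1 say that relatedness must be recorded before unblinding.
4. Possible correction: Section 9.2 provides for an independent relatedness assessment by the sponsor, which may upgrade the investigator's opinion but may not downgrade it when deciding whether an event is a SUSAR. It is not said to replace the investigator's label in the analysis.
5. Use: Section 10.1.4 (dose selection) and Sections 3.6 and 9.4.1 (DSMB reporting).

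Each link is in the text.

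**Scale of one label**

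Inputs from Sections 3.1 and 10.2: 45 patients per active cohort and 45 on pooled placebo. One SAE whose label changes moves a group's related-SAE incidence by 1/45 = 2.2 percentage points.

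**How many patients could qualify**

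The protocol gives no SAE rate. Assume that 5% to 15% of patients have at least one SAE:

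- All patients: 270 × 0.05 = 13.5 and 270 × 0.15 = 40.5, so about 14 to 41.
- Per group of 45: 45 × 0.05 = 2.25 and 45 × 0.15 = 6.75.

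These are counts of patients eligible for a code break. They are upper bounds on the number unblinded without clinical need, since an investigator may leave the code closed, and some code breaks would be clinically needed.

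**Illustration of the bias**

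Assumed values, none from the protocol: the same true SAE risk (5% to 15%) on active and placebo, counting one SAE per affected patient. Expected related SAEs per group = 45 × SAE risk × fraction called related.

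| Labelling | Active, 5% to 15% risk | Placebo, 5% to 15% risk |
|---|---|---|
| 20% called related in both groups | 0.45 to 1.35 | 0.45 to 1.35 |
| 30% on active, 10% on placebo | 0.675 to 2.025 | 0.225 to 0.675 |

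The ratio in the second row is 0.30/0.10 = 3, although the true SAE risk is equal. This shows the direction and possible size of the distortion if labels did shift in that way. It does not estimate what will happen.

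**The case against.** The strongest reply is that the text gives the investigator an ability and imposes no duty, against a default of blinding to database lock, so the number of needless code breaks could be near zero. That stands, and it is why no expected number is claimed. A reader might take 14 to 41 as the number who will be unblinded without need; the documents do not support this, because it would require every SAE to lead to a code break and none to have had a clinical reason.

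A reader might also infer that the ranking of the five regimens is at risk. The mechanism does not show that. It acts on active against placebo and would push all active cohorts the same way. With 5:1 allocation, a blinded investigator already faces odds of 45/54 = 83% that a patient is on active drug, and the cohorts already differ openly in injection volume or dosing frequency. Learning the code is most informative for placebo patients, who do not enter a comparison between regimens.

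It is tempting to say that the relatedness label decides what the DSMB sees. It governs only the 24-hour route for SAEs. Section 3.6 also sends accrued safety data to the specialist members monthly and has the full board review all accumulated data quarterly.

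A reader might infer that an unblinded patient usually stays on study drug, with later reporting affected. The protocol does not say whether dosing continues after a code break, so that is left out.

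Further limits are fair. Section 10.6.2.1 summarises all treatment-emergent SAEs as well as the potentially related ones, so an unfiltered count is available as a check. Dose selection sets no threshold on related SAEs and also weighs efficacy, platelet reductions, and renal or hepatic injury. The Safety Management Plan named in Section 9.1, or the IXRS instructions, may already prescribe the order of causality recording. That would ease the second part of the concern, but it would not change the stand-alone SAE condition in Section 4.4.

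**Conclusion.** The point holds as a potential bias in one comparison. Section 4.4 makes an SAE sufficient for investigator unblinding, nothing in the protocol puts the relatedness judgement first, and the related-SAE count is a named input to dose selection. The certain part of the size is that each relabelled event shifts a 45-patient group by 2.2 percentage points. The number of such events cannot be derived from the protocol; the eligible range rests wholly on the assumed SAE rate. Percent change in Lp(a) and the platelet-count criteria come from the laboratory and are largely unaffected, as are the all-SAE summary and the periodic DSMB reviews. No effect on regimen ranking is shown. Minor severity, worth correcting because it is cheap.

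**What to change.** In Section 4.4, delete the stand-alone SAE condition, so that investigator unblinding requires that knowledge of the assignment will affect the clinical management of the patient. Add that the investigator records causality before opening the code unless delay could harm the patient. Log the reason and time of every code break, and flag in the safety outputs any SAE whose relatedness was judged after unblinding. Emergency access is kept in full by the remaining condition, and SUSAR unblinding by the sponsor's drug safety personnel is unchanged.

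The cost is one or two sentences in the protocol, a confirmation prompt in the IXRS, and a small added documentation step for sites.

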### **5. PATIENT ELIGIBILITY**

To be eligible to participate in this study candidates must meet the following eligibility criteria at within 4 weeks of Study Day 1 or at the time point specified in the individual eligibility criterion listed.

#### **5.1 Inclusion Criteria**

1. Must have given written informed consent (signed and dated) and any authorizations required by local law and be able to comply with all study requirements
2. Males or females aged  $\geq 18$  and  $\leq 80$  years old at the time of informed consent
3. Clinical diagnosis of CVD defined as documented coronary artery disease (CAD), stroke, or peripheral artery disease
4. Lp(a) plasma level  $\geq 60$  mg/dL
5. Must be on standard-of-care preventative therapy for other than elevated Lp(a) CVD risk factors
6. Patients on the following medications must be on a stable regimen for at least 4 weeks prior to Screening and expected to remain on a stable regimen through the end of the post-treatment follow-up period:
  - a. lipid lowering drugs (statins, ezetimibe, proprotein convertase subtilisin/kexin type 9 [PCSK9s] inhibitors, niacin, fibrates, fish oil or other products containing omega-3 fatty acids including OTC preparations)
  - b. antiplatelet drugs
  - c. testosterone, estrogens, progesterone, growth hormone or progestins
7. Females: must be non-pregnant and non-lactating and either:

- a. surgically sterile (e.g., tubal occlusion, hysterectomy, bilateral salpingectomy, bilateral oophorectomy)
- b. post-menopausal (defined as 12 months of spontaneous amenorrhea in females > 55 years of age or, in females ≤ 55 years, 12 months of spontaneous amenorrhea without an alternative medical cause and FSH levels in the postmenopausal range for the laboratory involved)
- c. Abstinent\* or
- d. if engaged in sexual relations of child-bearing potential, agree to use 2 highly effective contraceptive methods (refer to [Section 6.3.1](#)) from the time of signing the informed consent form until at least 16 weeks after the last dose of Study Drug (ISIS 681257 or placebo)

\* Abstinence is only acceptable as true abstinence, i.e., when this is in line with the preferred and usual lifestyle of the patient. Periodic abstinence (e.g., calendar, ovulation, symptothermal, post-ovulation methods), declaration of abstinence for the duration of a trial and withdrawal are not acceptable methods of contraception

8. Males must be surgically sterile or, if engaged in sexual relations with a female of child-bearing potential, the patient must be using an acceptable contraceptive method (refer to [Section 6.3.1](#)) from the time of signing the informed consent form until at least 16 weeks after the last dose of ISIS 681257

## 5.2 Exclusion Criteria

1. Within 6 months of Screening: acute coronary syndrome, major cardiac surgery, or stroke/transient ischemic attack
2. Within 3 months of Screening: coronary, carotid, or peripheral arterial revascularization, major non-cardiac surgery, or lipoprotein apheresis
3. Heart failure New York Heart Association (NYHA) class IV
4. Uncontrolled hypertension (systolic > 160 or diastolic > 100 mm Hg)
5. History of acute kidney injury within 12 months of Screening
6. Uncontrolled hyper or hypothyroidism
7. Active infection requiring systemic antiviral or antimicrobial therapy that will not be completed prior to Study Day 1
8. Known history of or positive test for human immunodeficiency virus (HIV), hepatitis C or chronic hepatitis B
9. Malignancy within 5 years, except for basal or squamous cell carcinoma of the skin or carcinoma *in situ* of the cervix that has been successfully treated
10. Patients with a history of major bleed or high-risk of bleeding diathesis
11. Recent history of, or current drug or alcohol abuse
12. Known history or presence of systemic allergic or pseudoallergic (drug) reactions

13. Hypersensitivity to the active substance or to any of the excipients
14. Clinically-significant abnormalities in screening laboratory values that would render a patient unsuitable for inclusion, including the following:
  - a. Urine protein/creatinine ratio (UPCR)  $\geq 0.25$  mg/mg. In the event of a UPCR above this threshold, eligibility may be confirmed by a quantitative total urine protein measurement of  $< 300$  mg/24-hr
  - b. Urine albumin/creatinine ratio (UACR)  $\geq 100$  mg/g. In the event of a UACR above this threshold, eligibility may be confirmed by a quantitative total urine albumin measurement of  $< 150$  mg/24-hr
  - c. Estimated GFR  $< 60$  mL/min (as determined by the Chronic Kidney Disease-Epidemiological Collaboration (CKD-EPI) Equation for creatinine clearance
  - d. Alanine aminotransferase (ALT) or aspartate aminotransferase (AST)  $> 2.0$  x ULN
  - e. Bilirubin  $> ULN$ , unless prior diagnosis and documentation of Gilbert's syndrome in which case total bilirubin must be  $\leq 3$  mg/dL
  - f. Alkaline phosphatase (ALP)  $> ULN$
  - g. Platelet count  $< LLN$
15. Use of warfarin, direct thrombin inhibitors or factor Xa inhibitors
16. Treatment with another investigational drug, biological agent, or device within 1 month of Screening, or 5 half-lives of investigational agent, whichever is longer
17. Treatment with any non-Ionis oligonucleotide (including small interfering ribonucleic acid [siRNA]) at any time or prior treatment with an Ionis oligonucleotide or siRNA within 9 months of screening. Patients that have previously received only 1 dose of an Ionis oligonucleotide as part of a clinical study may be included as long as  $\geq 4$  months has elapsed since dosing
18. BMI  $> 40$  kg/m^2
19. Blood donation of 50-499 mL within 30 days of Screening or of  $> 499$  mL within 8 weeks of Screening
20. Unwillingness to comply with study procedures, including follow-up, as specified by this protocol, or unwillingness to cooperate fully with the Investigator
21. Have any other conditions, which, in the opinion of the Investigator or Sponsor would make the patient unsuitable for inclusion, or could interfere with the patient participating in or completing the Study

